Title:

Impact of Tourniquet Use on Functional Outcomes and Complications after TKA

Principal Investigator:

[name]

Co-Investigators:

[name]

[name]

[name], PT, DPT, MSCI

[name]

OVERVIEW

Background information:

Functional recovery after total knee arthroplasty (TKA) has seen dramatic improvement over the past 20 years through advances in surgical technique, implant design, perioperative pain management strategies, and physical therapy protocols. Tourniquet use during TKA, however, remains controversial due to conflicting reports in the literature on these benefits and risks of its use. Reported advantages of tourniquet use include improved visualization of the surgical field and decreased intraoperative blood loss. (Austin, 2019) Reported disadvantages of tourniquet use include increased postoperative pain and slower functional recovery as a direct result of the pressure of the tourniquet on the thigh during the procedure. (Ejaz 2014, Harsten 2015)

Traditionally with tourniquet use during TKA, the limb is exsanguinated and the tourniquet is raised to a fixed, pressure at the beginning of the case, typically 250mmHg to 350mmHg, and let down after closure. A novel tourniquet design that adjusts the tourniquet pressure in real-time based on intraoperative patient blood pressure measurements. This design may allow for the tourniquet to be inflated at a lower mean pressure while still maintaining efficacy.

A prospective study comparing total blood loss, pain and functional recovery after TKA using this novel tourniquet design, design (Zimmer A.T.S.® 4000TS Automatic Tourniquet System, with disposable contour cuffs) and TKA without tourniquet would further the current literature. Total blood loss will be calculated by previously validated methods. Pain and functional recovery will be closely monitored throughout the postoperative period using a patient wearable activity tracker (FitBit Inspire HR) and a smartphone-based patient engagement platform with integrated digital

surveys paired with smart-brace based home PT assessments (FocusMotion). Pain and functional recovery will be closely monitored throughout the postoperative period using a patient wearable activity tracker (FitBit Inspire HR) and a smartphone-based patient engagement platform with integrated digital surveys paired with smart-brace based home PT assessments (FocusMotion). Applying this technology to the proposed study can help identify problematic pain that is not appreciable during admission; given the fact that markers of inflammation and myocyte damage increase over time until at least post-operative day 3, it is possible that TKAs performed under tourniquet may have pain and narcotic requirements not appreciated with short-stay admissions (Huang 2014). The proposed study will further the literature on pain and narcotic use in the early time period after TKA, and will help identify if tourniquet has an effect on these variables.

Furthermore, sleep quality is a component of functional recovery and is correlated with pain. Knee osteoarthritis affects general quality of life by increasing sleep disturbance and nighttime wakening, and this is correlated with the pre-operative radiographic severity of disease (Sasaki, 2014). Sleep quality is affected in the immediate post-operative period after TKA as well, but improves by 3-6 months post-operatively (Chen, 2016). The proposed study would be the largest prospective study investigating the effect of TKA on pain and sleep quality, as well as being the first to investigate tourniquet use as a factor affecting sleep quality and pain. The proposed study would be the first to collect both subjective and objective data on the subject, using validated survey measurements as well as the data collected by the Fitbit Inspire HR device.

Research objectives:

The purpose of this study is to determine the effect of novel pressure-regulating tourniquet use on pain, functional recovery, sleep and total blood loss following total knee arthroplasty.

Specific Aim 1: Our primary aim is to determine the effect of tourniquet use on pain after TKA. Pain levels and oral analgesic requirements will be assessed daily using the FocusMotion remote patient monitoring platform.

Specific Aim 2: Secondary aim to determine the effect of tourniquet use on functional recovery after TKA. To do so, we will use a combination of standardized clinical assessments performed by physical therapy preoperatively and at 3 months postoperatively, as well as assessments with patient reported outcome surveys and functional assessments at regular intervals using the FocusMotion remote patient monitoring and virtual physical therapy platform.

Specific Aim 3: The third aim is to investigate sleep quality in the post-operative period after TKA with and without tourniquet use. We will apply both subjective measurements using the Pittsburgh Sleep Quality Index (PSQI) as well as sleep quality data as collected by the Fitbit HR.

Specific Aim 4: The fourth aim is to determine the effect of tourniquet use on total calculated blood loss after total knee arthroplasty. Hemoglobin dilution will be utilized to determine calculated blood loss using a validated methodology.

Potential Contribution: This study would give us a better understanding of the effect of a pressure auto-regulating tourniquet on pain, functional recovery sleep, and blood loss after total knee arthroplasty.

METHODS

Timeline: 3 years (2 years of prospective enrollment, 3 months years of follow-up for all participants, approx. 9 months of data analysis)

Inclusion/Exclusion criteria: The Principal Investigator (PI) will independently review all cases to confirm study eligibility for each patient. The following inclusion and exclusion criteria will be used to determine patient eligibility.

Inclusion criteria:

1. Age 18 and up
2. Primary unilateral TKA
3. BMI<45
4. Primary diagnosis of osteoarthritis
5. Patient has a iOS or Android smartphone capable of running FitBit and FocusMotion applications

Exclusion criteria:

1. Revision TKA
2. Bilateral TKA
3. Pregnancy
4. Prisoners
5. Pre-existing functionally-limiting neurologic disorder
6. Narcotic dependence, defined as oxycodone/hydrocodone use >5days/week
7. History of unprovoked VTE/PE
8. Inability to complete baseline functional testing

Recruitment: We will be recruiting patients from the clinical practices of [name], [name] and [name].

Design: The proposed study is a prospective, single blinded, randomized clinical trial with 2 study groups

For purposes of randomization, patients will be randomized into one of two groups tourniquet or no tourniquet, stratified by surgeon, using randomization sequences generated a priori using a computerized formal probability model with a block design and 1:1:1:1 allocation ratio. Patients will

be blinded to study group membership. As a result of the blocking, the desired allocation ratio will be maintained at periodic intervals throughout the recruitment process. The randomization sequences will be uploaded to REDCap so that allocations will be elicited using the REDCap randomization module in the immediate pre-operative period to minimize loss to follow-up.

Number of participants:

A pre-hoc power analysis for the primary outcome measure of VAS pain score was performed. A medium effect size of 0.5, power of 0.8, and alpha error of 0.05 were used for the analysis. With these assumptions, 128 patients were required to be enrolled in the study. With the dropout rate assumed to be 10%, 144 patients will be enrolled in the study.

Data collection:

Data collection will be done preoperatively, intraoperatively, 4 weeks post operatively, and at 12 weeks post operatively and at 1 year postoperatively. The data will be analyzed by site staff. All data to be collected can be found in tables 1-8.

All procedures will be performed by three surgeons ([name]) within a single institution at one site (Barnes Jewish West County and Progress West Hospital).

All participants will undergo standard admission and pre-operative procedure for primary total knee arthroplasty per institution protocol. Participants will be admitted to hospital on day of surgery for elective procedure. Spinal anaesthesia will be placed in pre-op holding area per regional anaesthesia team. Participants will be positioned in standard supine position. Per operative protocol each patient will undergo standard prep and drape. There will be no application of tourniquet for those randomized to no-tourniquet arm. If tourniquet is to be used, it will be applied after induction and will be deflated after incision closure. Maximum tourniquet time will be 120 mintues, TKA implant choice will be made based on surgeon preference. Transexamic acid will be given 1g IV prior to incision and 1g IV at end of case. The procedure for all participants will be via midvastus approach to the knee. At the end of the procedure, all patients will receive standard ipericapsular injection of 30mL 0.25% Marcaine with epinephrine and 30mL toradol prior to closure.

PT treatment and evaluation will take place on day of surgery post-operative day one prior to discharge. All patients will be placed on Aspirin EC 325mg BID for VTE prophylaxis. Pain medications will be standardized during admission, and an uncontrolled pain protocol will be available for implementation at physician discretion; see Tables 1 and 2) The final set of standard blood labs will be drawn at midnight. Discharge medications will be standard(Table 3)., Patients will be contacted at 1 week post-operatively to evaluate clinical progress, general concerns and compliance with study protocols, including use of the Fitbit HR platform and FocusMotion platforms.

Participants will be scheduled for a standard clinical visit at 4 weeks.

Participants will undergo final clinical evaluation at 3 months post-operatively with a PT visit and phone call from the research team as well as a final questionnaire about their experience with the app and Fitbit and knee brace which will be completed by paper, phone, or electronically.

Fitbit Activity Tracker and Focus Motion knee brace apps

During the pre-operative arthroplasty class, participants in the study will be set-up with a FitBit wrist-based activity tracker and FocusMotion knee brace and the appropriate software. Participants will be instructed to use the device in the 2 weeks prior to undergoing surgery, to gather baseline data on narcotic use, pain, use of assistive device and sleep quality. They will continue to use the devices for 3 months postoperatively(Table 7).

Subject Payment

Honorarium of \$100 provided at 3 months following completion of 3 month evaluation. Participants will be gifted the Fitbit Inspire HR and the FocusMotion smart-brace and platform and given an honorarium of \$50 for completion of the 1 year app based survey.

Participants Lost to follow-up: Some participants will not return for follow-up at the required intervals. A member of the research team shall contact non-respondent participants using phone calls, regular mail, e-mail, certified letters, or other means to urge participants to return for clinic follow-up or ascertain if a participant has moved, died, or otherwise become lost to follow-up. The following flow chart identifies the steps for attempts to locate lost participants. These actions, along with any other options available to the site, should be followed to exhaust all reasonable means in locating lost participants. These actions should be documented in the participant's records and may be performed concurrently or in parallel.

Phone call to last known number → Contact → Follow-up with participant

↓

No Contact

↓

Phone call to other numbers (spouse, relative, etc.) → Contact → Follow-up with participant

↓

No Contact

Note: There will be a minimum of 3 calls to different numbers

↓

Mail letter to last known patient address → Contact → Follow-up with participant

↓

No Contact

↓

Mail letter to secondary addresses → Contact → Follow-up with participant
↓
No Contact
↓
Mail “certified” type of letter to last address and any secondary address → Contact → Follow-up with participant
↓
No Contact
↓
Social Security Death Index to determine if participant has died → Confirm death
↓
Not Confirmed
↓
End attempts.

INFORMED CONSENT

Enrollment and consent will begin in the clinics of [name], [name] and [name], and will be the same for both study groups. The consent process will occur by one of the following means:

1) The study coordinator will meet with each potentially eligible participant to review the study requirements (including additional screening for eligibility) and answer any questions the patient may have.

If the patient has any clinical questions that cannot be answered by the study coordinator they will be answered by the physician or the physician's nurse. The patient will have the opportunity to review the consent form, discuss with family/friends, and do his/her own research on the subject if desired. Qualified patients who agree to participate in the study will be required to sign an Informed Consent Document. Valid enrollment is not granted until after surgery, once it has been verified that the participant qualifies for total knee replacement.

2) The consent discussion and review of the Informed Consent Document may occur over the phone. In this case, the study coordinator will call the patient to present the study to the participant and gauge interest in participation. If the patient expresses interest in participation, the study coordinator will e-mail, mail or fax the Informed Consent Document to the participant. The patient will be given the opportunity to ask questions. If the patient has any research questions beyond the scope of the study coordinator, arrangements will be made for the participant to speak with the applicable member of the research team, including the PI. After review of the Informed Consent Document, the participant will sign the applicable sections of the Informed Consent Document and email, mail or fax the consent form back to the study coordinator. The Informed Consent Document will be signed by the consenting study coordinator upon receipt. Valid enrollment is not granted until

after surgery.

PROCEDURES FOR MAINTAINING CONFIDENTIALITY

Data Security: Hard copies of patient questionnaires and CRFs will be stored in individual patient binders. The binders will be kept in a locked filing cabinet in an office that has password protected access and is locked when not in use.

Data collected on questionnaires and CRFs will be entered into electronic databases for analysis and tracking. These databases are on a secure server and can only be accessed by authorized research team members. There is no intention that the electronic records will be transported. We will not use laptops/jump drives/CD/DVDs to store, analyze, or input this data.

For data collected by the Fitbit platform including health monitoring and app-generated data, pre-assigned study ID numbers and anonymous email addresses will be used for all patient-reported and patient-generated data collection and transmission. No ePHI is seen or handled by the smartphone application or its data collection platform. The electronic key will be available only to the study team, not the mobile health platform or app developers.

De-identification of Data: All information will be collected by the research team in a confidential manner. PHI will be de-identified. All data will be entered into a master database that is password and security protected. Only members of the research team will be able to access information on study participants. Electronic key linking participant to data will be kept on a secured, password-protected network. All electronic information will be encrypted and stored in a password-protected database. All research files will be kept in a secure, locked location which can only be accessed by the study team. Once all manuscript submission is complete, all study documents, including the master list, will be retained for seven years after close of the study.

ASSESSMENT OF RISKS AND BENEFITS

There is a slight risk that patients may feel a small amount of psychological discomfort answering the questionnaires.

In addition there is the risk of breach of confidentiality.

Benefits: Participants will receive no direct medical benefit from study participation. However, this prospective study is the first to investigate tourniquet use as a factor affecting sleep quality and pain by collecting both subjective and objective data on the subject that is not be appreciable during admission. Furthermore, the study device design of adjusting tourniquet pressure in real-time based on intra-operative patient data measurements may allow for the tourniquet to be inflated at a lower mean pressure while still maintaining efficacy.

G1. Tables

Table 1: Post-operative pain protocol

Medication	Dose and Route	Timing	PRN
Percocet 5mg/325mg	1-2 tablets PO	Q6 hours	Yes
Toradol	30mg IV	Q6 hours	No
Morphine	2-4 mg IV	Q4 hours	Yes

*Toradol withheld in patients with sulfa allergy

Table 2: Discharge medication protocol

Medication	Dose and Route	Timing	Duration/PRN
Aspirin	325mg PO	BID	6 weeks
Percocet 5mg/325mg	1-2 tablets PO	Q6 hours	PRN
Celebrex*	200mg PO	BID	5 days
Senna-docusate	8.6mg/50mg PO	BID	PRN

*Celebrex withheld in patients with sulfa allergy

Table 3: Pre-operative data within 4 weeks of procedure

Test	Unit	Collected by
Knee circumference	cm	PT measurement
Passive Knee ROM	degrees	PT measurement
Active Knee ROM	degrees	FocusMotion Brace
Balance: tandem stance	scale	PT measurement
Balance: Standing on one leg	Scale	PT measurement
10m walk test for speed	Seconds	PT measurement
6 minute walk test	Meters	PT measurement
Timed up and go test	seconds	PT measurement
5 times sit to stand	Seconds	PT measurement
30 sec chair stand test	count	PT measurement
Timed Stair climb	seconds	PT measurement
Quadriceps strength	N	PT measurement
Hamstrings strength	N	PT measurement
Pittsburgh Sleep Quality Index	scale	FocusMotion App Survey
Oxford knee score	scale	FocusMotion App Survey
FJS	scale	FocusMotion App Survey
Visual Analog Scale pain score thigh	scale	FocusMotion App Survey
Visual Analog Scale pain score knee	scale	FocusMotion App Survey

Visual Analog Scale pain score leg/calf	scale	FocusMotion App Survey
% normal knee	Scale	FocusMotion App Survey
Use of assistive device	incidence	FocusMotion App Survey
Narcotic requirement, daily	Daily MME/hr	FocusMotion App survey
Sleep duration	min	Fitbit
Sleep quality (REM sleep/non-REM sleep)	percentage	Fitbit
Sleep disturbances	count	Fitbit
Sleep efficiency(time asleep/time in bed)	percentage	Fitbit
Charleston Comorbidity Index	Score	EPIC CPAP documentation
PROMIS	Score	WUPRO

Table 4: Intra-operative data during procedure

Test	Unit	Collected by
Tourniquet time		Surgeon
Tourniquet pressure		Surgeon
Length of surgery		Surgeon

Table 5: Post-operative data during hospital stay

Test	Unit	Collected by
Length of stay	Hours	Chart review
Day of discharge	number	Chart review
Total calculated blood loss	mL	Chart review
Occurrence of transfusion	incidence	Chart review
VAS pain score (q8hr)	scale	Nursing
Narcotic requirements, PACU to discharge	MME/hr	Chart review
Perioperative complications	incidence	Chart review

Table 6: Daily data points, from postop day 0 to 12 weeks postop

Data	Unit	Collected by
VAS pain score	Scale	FocusMotion App Survey
Total prescribed morphine equivalents	Pills/day	EPIC
Narcotic requirement, daily	MME/hr	FocusMotion App Survey
Sleep duration	Min	Fitbit
Sleep disturbances	Count	Fitbit

Table 7: Post-operative data at 3 months following procedure

Knee circumference	cm	PT measurement
Passive Knee ROM	degrees	PT measurement
Active Knee ROM	degrees	FocusMotion Brace
Balance: tandem stance	scale	PT measurement
Balance: Standing on One Leg	scale	PT measurement
10m walk test for speed	seconds	PT measurement
6 minute walk test	meters	PT measurement
Timed up and go test	seconds	PT measurement
5 times sit to stand	seconds	PT measurement
30 sec chair stand	count	PT measurement
Timed stair climb	seconds	PT measurement
Quadriceps strength	N	PT measurement
Hamstrings strength	N	PT measurement
PSQI	scale	FocusMotion App Survey
Oxford Knee Score	scale	FocusMotion App Survey
% normal knee	scale	FocusMotion App Survey
FJS	scale	FocusMotion App Survey
VAS pain score	scale	FocusMotion App Survey
Use of assistive device	incidence	FocusMotion App Survey

Narcotic requirement	daily MME/hr	FocusMotion App Survey
Sleep duration	min	Fitbit
Sleep disturbances	count	Fitbit
Sleep efficiency (time asleep/time in bed)	percentage	Fitbit
Sleep quality (REM sleep/non-REM sleep)	percentage	Fitbit
PROMIS	score	WUPRO
Wound complications	incidence	EPIC documentation
DVT/PE	incidence	incidence
Infection	incidence	EPIC documentation
Return to OR	incidence	EPIC documentation
Patient questionnaire about app and Fitbit/brace usage	questionnaire	Paper questionnaire or through app

REFERENCES

Dennis, D. A. ;Kittelson, A. J. ;Yang, C. C. ;Miner, T. M. ;Kim, R. H. ;Stevens-Lapsley, J. E. Does Tourniquet Use in TKA Affect Recovery of Lower Extremity Strength and Function? A Randomized Trial. 2016. Clin Orthop Relat Res; 474(1): 69-77

Huang, Z. Y. ;Pei, F. X. ;Ma, J. ;Yang, J. ;Zhou, Z. K. ;Kang, P. D. ;Shen, B. Comparison of three different tourniquet application strategies for minimally invasive total knee arthroplasty: a prospective non-randomized clinical trial. 2014. Arch Orthop Trauma Surg; 134(4): 561-70.

Kageyama, K. ;Nakajima, Y. ;Shibasaki, M. ;Hashimoto, S. ;Mizobe, T. Increased platelet, leukocyte, and endothelial cell activity are associated with increased coagulability in patients after total knee arthroplasty. 2007.

J Thromb Haemost; 5(4); 738-45

Liu, D. ;Graham, D. ;Gillies, K. ;Gillies, R. M. Effects of tourniquet use on quadriceps function and pain in total knee arthroplasty. 2014. Knee Surg Relat Res; 26(4); 207-13.

Nishiguchi, M. ;Takamura, N. ;Abe, Y. ;Kono, M. ;Shindo, H. ;Aoyagi, K. Pilot study on the use of tourniquet: a risk factor for pulmonary thromboembolism after total knee arthroplasty? 2005. Thromb Res; 115(4); 271-6.

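### Only patients are named as blinded, so the therapists who score the 3-month tests for Aim 2 are not protected from knowing the arm; analyst masking is a separate, smaller gap.

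*Combined protocol and SAP*

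**What the plan says.** The Design paragraph under Methods calls the study a "prospective, single blinded, randomized clinical trial" with two arms, and says that patients will "be blinded to study group membership". No other role is described as blinded anywhere in the document. The only mention of double blinding is in the title of a cited study in the reference list.

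Specific Aim 2 (functional recovery) draws on two kinds of data:

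- "standardized clinical assessments performed by physical therapy preoperatively and at 3 months postoperatively";
- "patient reported outcome surveys and functional assessments at regular intervals using the FocusMotion remote patient monitoring".

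The 3-month contact is described as a "final clinical evaluation at 3 months post-operatively with a PT visit and phone call from the research team". Table 7 lists what is collected then, and assigns 12 of its rows to measurement by physical therapy, for example "Timed stair climb".

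On analysis, the Data collection paragraph says: "The data will be analyzed by site staff". It does not say whether they see the arm labels. Table 4 has the surgeon record tourniquet time and pressure as study data. The confidentiality section restricts access to the research team, but does not separate allocation data from those who test patients or analyse results.

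**The concern.** Blinding the patient does not control what the tester does. In a walk, chair-stand, stair or strength test, the tester gives the instructions and encouragement, runs the watch or device, and decides what counts as a valid attempt. Balance scales and passive range of motion also depend on the tester's reading. A tester who knows the arm can shift these results without intending to. Randomisation does not remove such a shift, because it enters after allocation.

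The plan supplies a possible direction of expectation: its Background section lists slower functional recovery among the reported disadvantages of a tourniquet. Functional outcomes are also named in the trial title, so readers will look at these tests.

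Baseline testing is less of a worry. Allocation is drawn in the immediate pre-operative period, so tests completed before then cannot be influenced by it. For the same reason, adjusting for baseline would not correct a bias that arises only at 3 months.

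**Working it through.** **1. Who is masked, set beside who measures.**

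| Role | Task | Masking stated? |
|---|---|---|
| Patient | App surveys, including daily pain | Yes (Design) |
| Physical therapist | 12 rows of Table 7 at 3 months | No |
| Site staff | Analysis (Data collection) | No |

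**2. Count of therapist-measured rows in Table 7.**

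- Balance: tandem stance, one-leg stance (2)
- Timed or counted performance: 10 m walk, 6-minute walk, timed up and go, five-times sit to stand, 30-second chair stand, stair climb (6)
- Strength: quadriceps, hamstrings (2)
- Tester-read joint measure: passive range of motion (1)
- Size measure: knee circumference (1)

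Total 2 + 6 + 2 + 1 + 1 = 12, of which 2 + 6 + 2 = 10 are most open to encouragement or scoring.

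**3. The plan's own sample size.** The section on number of participants gives effect size 0.5, power 0.8 and alpha 0.05 for VAS pain. A two-sided, two-sample t-test needs 63.77, so 64 per arm and 128 in total, which matches. With 10% dropout, 128 / 0.9 = 142.2, so 143, or 144 with equal arms, which also matches. Masking changes neither figure.

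**4. Illustration of what a tilt would do.** Inputs: n = 64 per arm (128 / 2, equal arms assumed), two-sided alpha 0.05, no true effect, and a systematic tester shift of b SD between arms. The values of b are assumptions; the document gives none.

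Standard error of a standardised difference = sqrt(2/64) = 0.177. Non-centrality = b / 0.177. The rejection probability comes from the non-central t distribution with 126 degrees of freedom.

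| b (assumed) | b / 0.177 | False-positive rate, one outcome |
|---|---|---|
| 0 | 0 | 5.0% |
| 0.1 | 0.57 | 8.7% |
| 0.2 | 1.13 | 20.2% |
| 0.3 | 1.70 | 39.1% |

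The normal approximation gives 8.7%, 20.5% and 39.6%. A larger sample does not help: at 72 per arm (all 144 retained) the t-test rates are 9.2%, 22.2% and 43.2%, because a fixed bias is detected more often as the standard error falls. A tilt in the other direction could equally hide a real difference.

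**The case against.** The strongest reply is that silence is not unblinding. No text gives the therapists the allocation. It is drawn in REDCap just before surgery, the surgeon records the tourniquet data, and a blinded patient should not be able to tell the tester the arm. This stands in part: the document shows only that testers may know. A reader might infer that they do know, or that Aim 2 is already biased, and the document supports neither. But the design is stated as single blind with one role named, so masking of testers is not merely an unwritten detail that can be presumed.

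Second, the percentages follow mechanically from assumed tilts. They need a shift in the same direction across patients and testers, and they borrow an alpha that the plan states only for the pain power calculation. This stands. They show sensitivity and are not an estimate.

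Third, the scope is limited. Aim 2 is secondary and also uses brace-measured active range of motion, the Oxford Knee Score, the FJS and the percent-normal-knee rating, which come from a device or from blinded patients. A reader might extend the worry to the whole of Aim 2, to the primary app-reported pain outcome or to the Fitbit sleep data. Tester bias does not reach those. Nor are all 12 rows function tests: knee circumference is not.

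Fourth, an analyst who knows the arm is a different matter from a tester who does. That is right. Analyst knowledge is not confined to Aim 2, and no size is offered for it here.

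Fifth, the document does not say who the 3-month therapists are, what records they can open, or whether they treated the same patients in hospital. This stands as a limit on how complete masking can be.

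**Conclusion.** The point holds in a limited form. As written, the plan does not protect the 3-month testers from knowing the arm. Ten effort- or scoring-dependent tests, plus passive range of motion, are exposed within the therapist-scored part of secondary Aim 2. Whether any bias would occur, and how large, cannot be determined from the document. The figures of about 9%, 20% and 39% per outcome rest on assumed tilts of 0.1, 0.2 and 0.3 SD, equal arms of 64, two-sided testing at 0.05 and no true effect.

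The primary outcome and the sample size are unaffected. This is a cheap improvement worth making before testing is done, because a tester's influence on a measurement cannot be removed afterwards. The absence of stated analyst masking is a separate gap with an equally simple remedy.

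**What to change.** **Testers**

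- State in the Design section that the therapists who perform the 3-month tests are masked to arm.
- Give them no access to the REDCap allocation or the Table 4 tourniquet fields, and instruct them not to open the operative note before testing.
- Use a fixed script for instructions and encouragement.
- Record every unmasking, with its cause.

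**Analysts, separately**

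- Have site staff work on arms coded A and B until the analyses are final.
- Withhold tourniquet time and pressure over the same period, since those fields reveal the arm whatever the labels say.

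Describe the trial as assessor- and analyst-blinded only once these steps are in place.

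**Cost.** Protocol wording and a modest amount of access-control work. No additional visit or patient is needed, and the steps do not themselves call for an extra assessor. The downside is occasional accidental unmasking, most likely where a tester also treated the patient in hospital; the unmasking record makes its extent visible.

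### The patient blind is the only stated guard on a self-reported pain primary, yet controls get no cuff; an uninflated cuff kept out of view would protect it cheaply

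*Combined protocol and SAP*

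**What the plan says.** METHODS, Design: "The proposed study is a prospective, single blinded, randomized clinical trial with 2 study groups". The same section says that patients will "be blinded to study group membership". No one else is named as blinded.

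METHODS, Number of participants: "A pre-hoc power analysis for the primary outcome measure of VAS pain score was performed". Research objectives, Specific Aim 1, says how pain is collected: "Pain levels and oral analgesic requirements will be assessed daily using the FocusMotion remote patient monitoring platform". Table 6 lists VAS pain as a daily app survey item to 12 weeks. Table 5 adds eight-hourly in-hospital scores collected by nursing.

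METHODS, Data collection, describes theatre. On anaesthesia: "Spinal anaesthesia will be placed in pre-op holding area per regional anaesthesia team". On the control arm: "There will be no application of tourniquet for those randomized to no-tourniquet arm". In the other arm the tourniquet is applied after induction and let down once the incision is closed. Every patient is prepared and draped in the standard way.

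The documents mention no sham or uninflated cuff, no screening of the cuff or pump, no sedation rule, and no instruction to staff not to reveal the arm. Two later patient contacts are described. The first is at 1 week: "Patients will be contacted at 1 week post-operatively to evaluate clinical progress, general concerns and compliance with study protocols". The second is the 3-month evaluation, with a questionnaire on the app, Fitbit and brace. Neither description mentions asking patients which group they think they were in.

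**The concern.** When the outcome is a pain score that the patient enters, the patient is the assessor, and only the patient's ignorance of the arm keeps expectation out of the score. Allocation just before surgery and standardised analgesia guard against other biases, not this one.

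The control procedure works against that blind. One arm has equipment on the thigh and a pump in use; the other has neither. A spinal anaesthetic blocks sensation in the leg, but does not by itself stop a patient from seeing or hearing the set-up. Cuff marks or thigh soreness could later give the arm away as well.

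The Background names pain from cuff pressure on the thigh as a reported disadvantage. A patient who learned the arm and held that expectation could score accordingly, and the result would look like a tourniquet effect. Other outcomes reported through the app are exposed too: PSQI, Oxford Knee Score, FJS, percentage normal knee and daily narcotic use.

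**Working it through.** **1. Reproduce the plan's sample size.** Inputs from Number of participants: effect size 0.5, power 0.8, alpha 0.05, dropout 10%.

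- Normal approximation, two-sided: n per arm = 2(1.960 + 0.842)² / 0.5² = 62.8, so 63 per arm (126 in all).
- Two-sample t-test, two-sided: 63.77, so 64 per arm, or 128. This matches the plan exactly.
- One-sided t-test: 50.15, so 51 per arm, or 102. This does not match, so two-sided is taken as intended; the plan does not state it.
- Dropout: 64 / 0.9 = 71.1, so 72 per arm, or 144. This matches.

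The sample size is sound, and better blinding would not change it.

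**2. Trace the protection for the primary outcome.**

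| Question | What the documents give |
|---|---|
| Who reports the primary outcome? | The patient, daily in the app; nurses collect in-hospital scores |
| Who is blinded? | Patients only |
| What differs in theatre? | Cuff and pump in one arm, nothing on the thigh in the other |
| What hides the difference? | Cuff placed after induction, draped field; nothing else stated |
| Is the blind checked? | No check described |

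**3. What a given bias would do.** The documents give no rate of unblinding and no size of expectation effect. Let b be an assumed difference in mean VAS between arms, in SD units, caused only by knowledge of the arm. Assume a simple two-sample comparison with 64 per arm.

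- Standard error of the difference = √(2/64) = 0.177 SD.
- Noncentrality = b / 0.177 = 5.66b.
- False-positive rate = Φ(−1.96 + 5.66b) + Φ(−1.96 − 5.66b).

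| Assumed b (SD) | Share of the 0.5 SD design effect | False-positive rate, no true effect |
|---|---|---|
| 0 | 0% | 5.0% |
| 0.05 | 10% | 5.9% |
| 0.10 | 20% | 8.7% |
| 0.15 | 30% | 13.6% |
| 0.20 | 40% | 20.5% |

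If the true effect is 0.5 SD, the nominal power by the normal approximation is 80.7%. A shift of 0.10 SD moves it to 92.4% if the bias adds to the effect, or 61.9% if it subtracts. At 0.20 SD the figures are 97.7% and 39.6%.

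**4. Cost of the remedy.** 144 enrolled in two equal arms gives 144 / 2 = 72 control patients, hence about 72 cuffs.

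**The case against.** The strongest reply is that unblinding is not demonstrated, and this stands. The cuff goes on after the anaesthetic, the field is draped, and a spinal would be expected to remove sensation from the thigh. Silence on sedation does not mean that patients are awake and watching. A reader might infer that the arms are plainly visible to the patient and the blind is broken; the text does not support that.

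Second, the direction of bias is assumed. The Background calls tourniquet use controversial, with conflicting reports, and the consent pages are not available, so what patients are told cannot be judged. This stands too, which is why power is shown for bias in both directions.

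Third, large bias figures are easy to produce. If 60% of the tourniquet arm learned their group and each reported 0.5 SD more pain, the shift would be 0.60 × 0.5 = 0.30 SD and the false-positive rate about 40%. That needs two high assumptions at once, neither from the documents, and should not be used to judge the importance of the point.

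Fourth, not everything is self-reported. In-hospital narcotic use comes from chart review and prescribed amounts from the electronic record; only the daily app measure is the patient's own report. Physical therapy tests and Fitbit data are also less exposed. None of these replaces the pain primary.

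Fifth, the cuff in controls is a design preference and only a partial one. It is partial, but it removes an avoidable difference in theatre at low cost.

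**Conclusion.** The point holds as a gap in design that is cheap to narrow. The patient blind is the only stated protection against reporting bias in the primary outcome, and the control procedure as written works against it. That patients could learn their arm is plausible, not shown.

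The size is conditional. If knowledge of the arm shifted reported pain by 0.05 to 0.20 SD between arms, with 64 per arm, a two-sided 5% test and no true effect, the false-positive rate would be about 6% to 20%. The shift is an assumption throughout; the documents can neither confirm nor exclude it.

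A reader might also infer that the trial should be called blinded only if patients' guesses fail to separate the arms. That does not follow. If a tourniquet really causes thigh pain, sore patients will guess correctly without any leak, and such a rule would count against a true effect. Nor can it be said that the existing contacts leave the question out: only their topics are given, and the instruments are not shown.

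**What to change.** **Main change.** In METHODS, Data collection, replace the sentence on the control arm with wording to this effect: the same contour cuff is placed on the thigh after induction in both arms; in the no-tourniquet arm it is left uninflated; cuff, pump and display are kept out of the patient's view throughout.

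Cost: a short amendment and about 72 extra disposable cuffs. Limit: an uninflated cuff reproduces neither pressure marks nor soreness, so unblinding after surgery is reduced, not removed.

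**Optional addition.** Ask patients before discharge, and again at the existing 1-week contact, which group they think they were in and why. Report the answers by arm beside the primary result, as descriptive context only, with no decision rule attached. The earlier question is less affected by accumulated symptoms, and the reason given helps to tell a patient who saw or heard the equipment from one who inferred the arm from pain. Cost: one two-part question asked twice. It can be added even if the sponsor does not adopt the cuff in controls.
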